11.2 Time Period and Frequency for Event Assessment and Follow-Up

Unanticipated problems will be recorded in the data collection system throughout the study.

The PI will record all adverse events with start dates occurring any time after informed consent is obtained until 28 days after the last EBRT treatment or 85 days after first treatment dose of CLR 131, whichever is later. At each study visit, the investigator will inquire about the occurrence

of AE/SAEs since the last visit. Events will be followed for outcome information until resolution or stabilization.

11.2.1 Adverse Events

- AEs will be recorded from time of informed consent until 28 days after last EBRT treatment or 85 days after first treatment dose of CLR 131, whichever is later.
- AEs will be recorded per the reporting time above regardless of whether or not they are considered related to the study drug(s).
- AEs will be recorded in the subject's medical record and on the appropriate study specific eCRF form within OnCore.
- All AEs considered related to study drug(s) will be followed until resolution to ≤ Grade 1 or baseline, deemed clinically insignificant, and/or until a new anti-cancer treatment starts, whichever occurs first. If the subject begins a new anticancer therapy, the AE reporting period for non-serious AEs ends at the time the new treatment is started.
- Only clinically significant laboratory abnormalities will be captured as adverse events on the appropriate study specific eCRF form within OnCore.

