3.2 Study Outcome Measures

3.2.1 *Primary*

- Incidence of adverse events assessed using Common Terminology Criteria for Adverse Events (CTCAE) version 5.0

3.2.2 *Secondary*

- Median radiation treatment time and median number of dose delays due to toxicity
- CLR 131 tumor uptake via SPECT/CT imaging and Monte Carlo calculations
- Overall response rate (ORR) defined as the proportion of subjects who experience either a partial response or complete response within 6 months post completion of EBRT as measured by standard of care imaging (e.g. CT, MR, PET-MR)
- Swallow function assessed by Dynamic Imaging Grade of Swallowing Toxicity (DIGEST) scale
- Quality of life (QoL) assessed by MD Anderson Dysphagia Inventory score (MDADI)
- Salivary flow rate related quality of life assessed by stimulated salivary flow

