8.2.1.1 Complete Blood Count with Differential

Blood will be drawn for CBC with differential at screening (standard of clinical care); weekly for 12 weeks beginning with day 1 treatment dose (research-related procedure); and at 3 months post EBRT (standard of clinical care).

The CBC will include red blood cell count, hemoglobin, hematocrit, WBC count with differential including % neutrophils, lymphocytes, monocytes, eosinophils and basophils, absolute neutrophil count, and platelet count.

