11.3.2 Expectedness

The Study PI will be responsible for determining whether an adverse event is expected or unexpected. An adverse event will be considered unexpected if the nature, severity, or frequency of the event is not consistent with the risk information previously described for the intervention.

There are expected significant toxicities and adverse events associated with CLR 131 treatment. The most significant toxicities associated with CLR 131 involve myelosuppression such as neutropenia, anemia, and thrombocytopenia, which in some cases are Grade 3 or 4. These adverse events are expected to occur within 4 weeks from the first CLR 131 dose and are expected to be resolved by approximately 65 days after the last treatment dose of CLR 131. Thus, the DLT period has been defined to account for the expected toxicities of CLR 131 in section 2.3.1.1.1

There are expected significant toxicities and adverse events associated with SOC EBRT. These toxicities include Grade 3 radiation mucositis and Grade 3 radiation dermatitis.

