14.2 Sample Size Considerations

An mTPI-2 design, an extension of modified toxicity probability interval (mTPI-2), will be used to identify the MTD using cohorts of 4 subjects and up to 3 dose levels of CLR 131 (Ji *et al.*, 2007; Ji & Wang, 2013). The first 4 subjects will be treated at Dose Level 1. The maximum number of subjects treated at a dose level will be 8, with one exception: if 1 out of 8 subjects experiences a DLT at Dose Level 1, the study team will consider the possibility of treating 2 additional subjects at Dose Level 1. The trial can be monitored using columns 4 and 8 of [Table 3](#) below, which contains the dose-escalation rules. Dose escalation will not be confirmed until all subjects in cohort recover to non-DLT levels or meet the criteria above. If 0 out of 4 subjects experiences a DLT at Dose Level 2, the study will move directly to the expansion phase.

Dose Level	Doses* of CLR 131
-1	12.5 mCi/m ²
1**	15.6 mCi/m ²
2	18.75 mCi/m ²

*Dose level listed is administered on first on day 1 and again on day 8.

**The first 4 subjects will be treated at dose level 1. Dose level -1 will be used as a de-escalation dose.

Table 3: Dose escalation rules

	1	2	3	4	5	6	7	8	9	10
0	E	E	E	E	E	E	E	E	E	E
1	D	D	D	S	S	S	S	S	S	E
2		DU	DU	D	D	D	S	S	S	S
3			DU	DU	DU	DU	D	D	D	D
4				DU	DU	DU	DU	DU	DU	D
5					DU	DU	DU	DU	DU	DU
6						DU	DU	DU	DU	DU
7							DU	DU	DU	DU
8								DU	DU	DU
9									DU	DU
10										DU

Column indicates the number of subjects treated. Row indicates the number of subjects with DLTs. **E**: Escalate to the next higher dose; **S**: Stay at the same dose; **D**: De-escalate to the previous lower dose; **DU**: De-escalate to the previous lower dose and the current dose will never be used again in the trial; sample size = **10**, target toxicity probability = **0.2**, epsilon 1 =**0.1**, epsilon 2 =**0.1**.

The number of participants treated in the expansion cohort is dependent on the number of participants treated at the MTD in the dose escalation phase using the the mTPI-2 design. Up to 12 subjects will be treated at the MTD. Statistical analysis for outcomes is based on participants treated at the MTD, including dose escalation patients treated at the MTD.

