14.3 Final Analysis Plan

14.3.1 Analysis of Primary Endpoints

Adverse events will be reported using frequency tables. Confidence intervals will be constructed using exact statistical methods (such as exact binomial confidence interval) due to small sample size.

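### Laboratory abnormalities become adverse events only through an undefined judgement, so the primary incidence table may omit cytopenias that the scheduled blood counts could grade

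*Combined protocol and SAP*

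**What the plan says.** - **Outcome.** Section 3.2 gives the primary outcome as: "Incidence of adverse events assessed using Common Terminology Criteria for Adverse Events (CTCAE) version 5.0".
- **Analysis.** Section 14.3.1 says: "Adverse events will be reported using frequency tables". It adds: "Confidence intervals will be constructed using exact statistical methods (such as exact binomial confidence interval) due to small sample size". Section 14.3 plans no summary of graded laboratory values.
- **Capture rule.** Section 11.2.1 says: "Only clinically significant laboratory abnormalities will be captured as adverse events on the appropriate study specific eCRF form within OnCore". Section 11 gives no grade threshold, definition or named decision-maker for clinical significance in this setting. Section 16.1 has physicians assign grades and attributions at clinic visits.
- **Broader text.** The AE definition in section 11.1.2 includes an abnormal laboratory finding. Section 11.1 requires that every new or worsening event after study drug be captured.
- **Expected toxicity.** Section 11.3.2 says: "The most significant toxicities associated with CLR 131 involve myelosuppression such as neutropenia, anemia, and thrombocytopenia".
- **Data available.** Section 8.2.1.1 schedules blood counts at screening, "weekly for 12 weeks beginning with day 1 treatment dose", and at 3 months after external beam radiation therapy (EBRT). Section 8.2.1.2 gives chemistries the same schedule. Section 18.3 keeps laboratory reports in the data management system.

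**The concern.** The toxicity of most interest is measured objectively on a fixed schedule, yet it reaches the primary table only if someone judges it clinically significant. Two physicians looking at the same asymptomatic low count could decide differently and both comply with section 11.2.1. The study is single-arm, so no comparator would absorb such differences. The reported incidence would then describe a mixture of toxicity and recording practice. The exact interval would not show this, because it reflects sampling error only.

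The main product of the trial is a description of how well the combination is tolerated at the maximum tolerated dose (MTD). An incomplete cytopenia profile would weaken that description for whoever plans the next study.

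**Working it through.** The plan states no AE rate, power or interval that depends on the capture rule, so there is no figure to reproduce. The check has three parts.

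**1. Where a cytopenia would be reported**

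| Output | Rule | Does it catch every graded cytopenia? |
|---|---|---|
| DLT (2.3.1.1.2) | Grade 4 for more than 4 weeks, or Grade 3 for more than 8 weeks | No, prolonged severe cases only |
| SAE (Table 2 footnote, 11.4.2) | A Grade 1 to 4 hematologic event manageable by transfusion is not an SAE unless it exceeds the DLT window | No |
| AE table (11.2.1, 14.3.1) | Entered only if clinically significant | Depends on the undefined term |

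Example: a Grade 4 thrombocytopenia that lasts three weeks and is managed with platelets is neither a DLT nor an SAE. The AE table is its only planned summary. It would probably be entered, but the text does not ensure that. An asymptomatic Grade 1 or 2 count is less certain still.

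**2. What omission would do (hypothetical)**

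Inputs: n = 12, the maximum under section 14.2 ("Up to 12 subjects will be treated at the MTD"). The interval level is not stated, so 95% is assumed. The true proportion of subjects affected (p) and the probability that an affected subject has the event entered (c) are assumptions, because the documents give neither.

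Exact (Clopper-Pearson) limits for x of n: lower = Beta(0.025; x, n − x + 1), upper = Beta(0.975; x + 1, n − x).

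- 6/12 = 50%, interval 21.1 to 78.9%
- 4/12 = 33%, interval 9.9 to 65.1%
- Each subject not entered moves the rate by 1/12 = 8.3 percentage points.

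With q = p × c, the reported count is Binomial(12, q). Coverage is the probability that the interval contains p. At p = 0.75 the interval contains p when x is 6 to 12, since the upper limit is 0.723 at x = 5 and 0.789 at x = 6, and the lower limit at x = 12 is 0.735. Coverage is then P(X ≥ 6 given q). The sets for p = 0.50 (x from 3 to 9) and p = 0.90 (x from 8 to 12) follow in the same way.

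| c | Reported rate at p = 0.75 | Coverage, p = 0.50 | Coverage, p = 0.75 | Coverage, p = 0.90 |
|---|---|---|---|---|
| 1.00 | 75% | 0.961 | 0.986 | 0.996 |
| 0.75 | 56% | 0.885 | 0.767 | 0.655 |
| 0.50 | 38% | 0.609 | 0.271 | 0.112 |
| 0.25 | 19% | 0.182 | 0.014 | 0.001 |

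The row c = 1 corresponds to grading every subject from the counts.

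**3. How much of the AE window the counts cover**

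- Twelve weekly draws, the first on day 1, end on day 1 + 7 × 11 = 78. With 12 subjects and no missed draw, that is 12 × 12 = 144 counts.
- The AE window closes at the later of 85 days after the first treatment dose (day 86) and 28 days after the last EBRT treatment.
- Without any reduction for CLR 131, EBRT takes 60/2.5 = 24 to 70/2.0 = 35 weekday fractions. A start 7 to 14 days after day 8 is day 15 to 22. Assuming a Monday start and no interruption, EBRT ends on day 46 to 68.
- 68 + 28 = 96, so the window closes between day 86 and day 96. The weekly counts miss its last 8 to 18 days.

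**The case against.** The strongest reply is that omission is possible but not shown.

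- No section makes expectedness a reason not to record an event. Section 11.2.1 records AEs whether or not they are considered related to study drug. The Table 2 footnote speaks of hematologic AEs of Grades 1 to 4, which sits poorly with routine omission.
- The judgement is also overseen. Section 11.1 names review of laboratory results as a source of AEs, Appendix A schedules AE evaluation at the safety monitoring visits, physicians sign the grading (16.1), each subject's results are discussed at regular team meetings (section 12), and monitors verify source data (section 13).
- The endpoint is descriptive, with no test or threshold in section 14.3.1 that a shift would cross. The two illustrative intervals overlap widely.

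Most of this stands, and it limits the point to what may be omitted. It does not supply a definition or a laboratory-graded summary.

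A reader might go further and infer that the filter distorts dose finding. The documents do not support that. DLTs rest on grade and duration with no significance test, and escalation is not confirmed until the cohort has recovered or met the DLT criteria, so severe counts have to be graded and followed anyway. Nor would a difference between an AE incidence and a duration-based DLT count be an error, because they measure different things.

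**Conclusion.** The point holds in a limited form. Section 11.2.1 puts an undefined judgement between the laboratory data and the primary endpoint, in tension with sections 11.1 and 11.1.2, and no other planned output summarises all graded cytopenias. The exposure lies mainly in lower-grade or asymptomatic cytopenia, and in shorter or transfusion-managed events that are neither DLTs nor SAEs.

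A reader might infer that the trial does under-count its main toxicity, or that 33% in place of 50% estimates the loss. Neither follows. The 4/12 and 6/12 figures and the coverage table rest on assumed values of p and c. They show only that at n = 12 a modest amount of non-entry would matter.

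The conclusion also assumes that CTCAE v5.0 grades can be derived from the stored values. The documents do not reproduce the thresholds, so this needs confirming for each parameter. The case for change rests on low cost and greater objectivity, not on a demonstrated bias.

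**What to change.** 1. **Add a table to section 14.3.1.** For each blood count and chemistry parameter, report the worst CTCAE v5.0 grade per subject derived from all scheduled values, with baseline-to-worst shift. Give exact intervals, at a stated level, for any grade and for Grade 3 or higher. Show it beside the investigator-reported AE table, which stays as it is.
2. **State the conventions.** Use the screening value as baseline, because the treatment day 1 value is drawn after the dosimetry test dose. Give the number of subjects with post-dose values, flag values drawn after the AE window (such as the 3-month post-EBRT sample), and list any parameter that cannot be graded from the value alone.
3. **Reconcile section 11.2.1 with sections 11.1 and 11.1.2.** Either define clinical significance for AE entry, or say that laboratory values are summarised separately and completely.

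The protocol summary dates the close of accrual to April 2022 and the end of the last DLT window to June 2022. Redefining the term now would therefore not change how those data were collected, whereas grading the stored values still can.

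**Cost.** No new blood draws and no change in sample size. Section 18.3 establishes that reports are kept, not that every value is in programmable form, so some data entry may be needed. Reported rates may look higher. The weekly counts end near day 78, so the last part of the AE window would still rest on investigator entry.

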11.2.2 Serious Adverse Events

- SAEs, both related or unrelated to the study, will be recorded from time of informed consent until 28 days after last EBRT treatment or 85 days after first treatment dose of CLR 131, whichever is later.
- Any SAEs experienced after this period will only be reported if the investigator suspects a causal relationship of possibly, probably or definitely related to the study treatment.
- SAEs will be reported on the SAE Submission Form and entered in SAE tab in OnCore within the timeframe listed in [Table 2](#).
- SAEs will be recorded in the subject's medical record and on the appropriate study specific eCRF form within OnCore.
- All SAEs, regardless of relation to study drug, will be followed until resolution to ≤ Grade 1 or baseline and/or deemed clinically insignificant and/or until a new anti-cancer treatment starts, whichever occurs first.
- Recurrent episodes, complications, or progression of the initial SAE will be reported as follow-up to the original episode within 24 hours of the investigator receiving the follow-up information.

Reporting and submission requirements are described in Section 11.4.

11.2.3 Other Reportable Events

Reporting timeframes begin when PI learns of the occurrence of the event.

Table 1: Other Reportable Events Timeframe

Event	Definition	Reporting
Breach of confidentiality	The exposure of any study information or communications directly related to a study subject to anyone not named as study staff or the release of a study subject's identifiable information to study staff who were not specified to receive such information in the protocol or IRB application.	Within 14 business days of knowledge of event
Protocol deviation	A deviation is an incident involving a departure from the IRB-approved protocol in the actual conduct of the study. Deviations may result from the action of the participant, investigator, or staff.	See details below
Major deviations	Deviations are considered major when the unapproved change(s) in previously approved research activities, implemented without IRB approval, may potentially adversely affect subjects' rights, safety, welfare, or willingness to continue participation, or affect the scientific design of the study and/or the integrity of the resultant data.	Within 14 business days of knowledge of event
Minor deviations	Deviations are considered minor when the unapproved change(s) in previously approved research activities, implemented without IRB approval, do not adversely affect subjects or the integrity of the study data.	Cumulative minor deviations are reported at the time of continuing review.
Protocol violation	An incident involving an intentional deviation from the IRB-approved protocol that was not implemented in response to an emergency situation and that may impact a subject's rights, safety, and/or welfare, makes a substantial alteration to risks to subjects, or affects the scientific design of the study and/or the integrity of the resultant data. Violations may also be repeated deviations (major or minor) of the same nature. Violations can represent serious or continuing non-compliance with the federal regulations and guidelines for ethical conduct of human subject research.	Within 14 business days of knowledge of event
Protocol Exceptions	A protocol exception is an IRB-approved deviation for a single subject or a small group of subjects but is not a permanent revision to the research protocol.	Protocol exceptions must be approved by local IRB prior to implementation.

11.3 Characteristics of an Adverse Event

11.3.1 Relationship to Study Intervention

The PI will determine the relationship of adverse events to the research intervention using the following scale:

- Definite = AE is definitely related to the study procedures
- Probable = AE is likely related to the study procedures
- Possible = AE is possibly related to the study procedures
- Unlikely = AE is doubtfully related to the study procedures
- Unrelated = AE is definitely not related to the study procedures

11.3.2 Expectedness

The Study PI will be responsible for determining whether an adverse event is expected or unexpected. An adverse event will be considered unexpected if the nature, severity, or frequency of the event is not consistent with the risk information previously described for the intervention.

There are expected significant toxicities and adverse events associated with CLR 131 treatment. The most significant toxicities associated with CLR 131 involve myelosuppression such as neutropenia, anemia, and thrombocytopenia, which in some cases are Grade 3 or 4. These adverse events are expected to occur within 4 weeks from the first CLR 131 dose and are expected to be resolved by approximately 65 days after the last treatment dose of CLR 131. Thus, the DLT period has been defined to account for the expected toxicities of CLR 131 in section 2.3.1.1.1

There are expected significant toxicities and adverse events associated with SOC EBRT. These toxicities include Grade 3 radiation mucositis and Grade 3 radiation dermatitis.

11.3.3 Severity of Event

Adverse events will be documented and recorded at each visit using NCI CTCAE version 5.0.

11.4 Reporting Procedures

11.4.1 Unanticipated Problem (UP) Reporting to IRB, Collectar and UWCCC DSMC

Incidents or events that meet the OHRP criteria for unanticipated problems require the creation and completion of an unanticipated problem report form. OHRP recommends that investigators include the following information when reporting an adverse event, or any other incident, experience, or outcome as an unanticipated problem to the IRB:

- appropriate identifying information for the research protocol, such as the title, investigator's name, and the IRB project number;
- a detailed description of the adverse event, incident, experience, or outcome;

- an explanation of the basis for determining that the adverse event, incident, experience, or outcome represents an unanticipated problem;
- a description of any changes to the protocol or other corrective actions that have been taken or are proposed in response to the unanticipated problem.

To satisfy the requirement for prompt reporting, unanticipated problems will be reported using the following timeline:

- Unanticipated problems that are serious adverse events will be reported to the IRB, Collectar Biosciences ([contact]) and to the UWCCC DSMC per [Table 2](#) timeline.
- Any other unanticipated problem will be reported to the IRB, Collectar Biosciences ([contact]) and the UWCCC DSMC per [Table 1](#) timeline.
- All unanticipated problems should be reported to appropriate institutional officials (as required by an institution's written reporting procedures), the supporting agency head (or designee), and OHRP within one month of the IRB's receipt of the report of the problem from the investigator.

11.4.2 Serious Adverse Event Reporting

Depending on the nature, severity, and attribution of the serious adverse event an SAE report will be phoned in, submitted in writing, or both according to [Table 2](#) below. All serious adverse events must also be reported to the UWCCC DSMC. All serious adverse events must also be reported to the UW IRB (if applicable), and any sponsor/funding agency not already included in the list.

SAEs experienced by a subject after the active reporting period has ended should be reported to Collectar Biosciences if the PI becomes aware of them; at a minimum, all SAEs that the PI believes have at least a reasonable possibility of being related to investigational product are to be reported to Collectar Biosciences.

Determine the reporting time line for the SAE in question by using the following table.

Table 2: FDA Reporting Requirements.

FDA Reporting Requirements for Serious Adverse Events (21 CFR Part 312)

NOTE: Investigators **MUST** immediately report to the UWCCC DSMC, Collectar Biosciences, and the IRB (if applicable) and any other parties outlined in the protocol ANY Serious Adverse Events, whether or not they are considered related to the investigational agent(s)/intervention (21 CFR 312.64).

An adverse event is considered serious if it results in ANY of the following outcomes:

- 1) Death.
- 2) A life-threatening adverse event (the subject was at risk of death at the time of the event; it does not refer to an event that hypothetically might have caused death if it were more severe).
- 3) An adverse event that results in inpatient hospitalization or prolongation of existing hospitalization for \geq 24 hours. *
- 4) A persistent or significant incapacity or substantial disruption of the ability to conduct normal life functions.
- 5) A congenital anomaly/birth defect.
- 6) Important Medical Events (IME) that may not result in death, be life threatening, or require hospitalization may be considered serious when, based upon medical judgment, they may jeopardize the subject and may require medical or surgical intervention to prevent one of the outcomes listed in this definition (FDA, 21 CFR 312.32; ICH E2A and ICH E6).

ALL SERIOUS adverse events that meet the above criteria **MUST** be immediately reported to Collectar and UWCCC DSMC within the timeframes detailed in the table below:

Hospitalization	Grade 1 and Grade 2 Timeframes	Grade 3-5 Timeframes
Resulting in hospitalization \geq 24 hrs	10 Calendar Days	24 Hour; 5 Calendar Days
Not resulting in Hospitalization \geq 24 hrs	Not required	

***Planned hospitalizations for disease-related surgery, routine procedures (such as G-tube placement), non-disease-related procedures, and inpatient hospitalization for radiation protection/exposure levels are not considered SAEs. A hematologic adverse event grade 1-4 will not be defined as an SAE if it can be managed with blood product transfusions, unless it exceeds the window for a dose limiting toxicity.**

Expedited AE reporting timelines are defined as:

- **24-Hour; 5 Calendar Days** – The AE must initially be reported within 24 hours of learning of the AE, followed by a complete expedited report within 5 calendar days of the initial 24-hour report.
- **10 Calendar Days** – A complete expedited report on the AE must be submitted within 10 calendar days of learning of the AE.

Serious adverse events that occur more than 28 days after last EBRT treatment or 85 days after first treatment dose of CLR 131, whichever is later and have an attribution of possible, probable, or definite require reporting as follows:

Expedited 24-hour notification followed by complete report within 5 calendar days for:

- All Grade 3, 4, and 5 AEs

Expedited 10 calendar day reports for:

- Grade 2 AEs resulting in hospitalization or prolongation of hospitalization

